- Task-based fMRI analyses will be repeated using a GLM in SPM to provide a map of task response as well as group-level effects on the task response.

STUDY METHODS

STUDY DESIGN

The QTT trial was a randomized, double-blinded, placebo-controlled, parallel-group, single-site clinical trial for 12 weeks (main trial) and a long-term follow-up 26 weeks after the intervention. The trial compared single-dose psilocybin therapy vs placebo therapy. The treatment involved two preparation sessions, a high-dose psilocybin session (25 mg) or placebo (inert substance) session, and three integration sessions. Baseline data was collected at screening visit and outcomes were assessed 1, 4, 8, 12 (primary endpoint) and 26 weeks after the psilocybin/placebo session. A sub-group of participants underwent fMRI scan 1 week after the intervention (no baseline scan).

RANDOMIZATION

The participants were randomized in two groups (1:1): psilocybin therapy or placebo therapy. The randomization was stratified in terms of age (20-45, 46-70 years), sex, and baseline alcohol consumption i.e. the number of heavy drinking days in the last 28 days before inclusion measured by the TLFB-method (5-15, 16-28 days). The randomization tool in REDCap was used. Patients, investigators, other caregivers performing assessments, and persons performing data analysis have been blinded from the time of randomization and until the time of database unlock.

SAMPLE SIZE

The study was initially designed to enroll 90 participants, based on an a priori power analysis informed by effect sizes reported in the open-label pilot study by Bogenschutz and colleagues (2015). Assuming a two-

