sided alpha level of 0.05 and 90% power, the required sample size was estimated to be 27 participants per treatment arm. Anticipating a dropout rate of approximately 40%, the total planned enrollment was therefore set at 90 participants. Due to delays associated with the COVID-19 pandemic and lack of financial resources to continue the study, recruitment was terminated before reaching the intended enrollment target. Following the decision to stop recruitment, a revised power calculation—based on the originally specified primary endpoint and the same effect size assumptions as the initial power analysis—indicated that 22 participants per treatment arm would provide approximately 85% power, corresponding to a total of 44 completers. As of December 2025, the observed dropout rate was substantially lower than anticipated (13%), resulting in 59 enrolled participants, of whom 51 completed the primary endpoint assessment. The number of completers therefore exceeded the minimum sample size required according to the revised power calculation. Of these, 28 completed fMRI scans, however only those with complete behavioural data and adequate quality imaging data for analyses will be retained for analyses. Imaging data will be quality controlled using fMRIPrep.

TRIAL POPULATION

Recruitment

Recruitment began September 2023 and ended September 2025. Last patient's last visit in the main trial i.e., the 12-week outcome assessment was on 22nd December 2025. Last patient's last visit concluding the entire study i.e., the 26-week follow-up will be end of March 2026. Participants were recruited in part from outpatient clinics, but predominantly from society via advertisement.

Eligibility

Treatment seeking individuals aged 20-70, weighing 60-95kg, diagnosed with AUD and alcohol dependence according to DSM-V and ICD-10, respectively, who had at least 5 heavy drinking days within the past 28 days of screening, and no co-occurring substance use disorders (except nicotine) and no concomitant pharmacotherapy for AUD.

OUTCOMES

OUTCOME CATEGORY	SOURCE	TIME POINTS	PRIMARY COMPARISON (BETWEEN-GROUP DIFFERENCE)
Primary			
1. Percentage of Heavy Drinking Days (PHDD)	TLFB/28 days	BL, W4, W8, W12	W12, adjusted for BL
Secondary			
2. Alcohol consumption:			
• % drinking days	TLFB/28 days	BL, W4, W8, W12	W12, adjusted for BL
• Drinks per day	TLFB/28 days	BL, W4, W8, W12	W12, adjusted for BL
• Drinks per drinking day	TLFB/28 days	BL, W4, W8, W12	W12, adjusted for BL

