Abbreviations: BL = baseline; W1, W4, W8, W12 = Week 1, Week 4, Week 8, and Week 12; PHDD = percentage of heavy drinking days; TLFB = Timeline Followback; WHO = World Health Organization; PEth = phosphatidylethanol; GGT = gamma-glutamyl transferase; ALAT = alanine aminotransferase; MCV = mean corpuscular volume; fMRI = functional magnetic resonance imaging; BOLD = blood oxygenation level-dependent; ROI = region of interest; BDNF = brain-derived neurotrophic factor; SETS = Stanford Expectancy Treatment Scale; PACS = Penn Alcohol Craving Scale; AUDIT = Alcohol Use Disorders Identification Test; DUDIT = Drug Use Disorders Identification Test; AASE = Alcohol Abstinence Self-Efficacy Scale; MDI = Major Depression Inventory; MAAS = Mindful Attention Awareness Scale; AAQ = Acceptance and Action Questionnaire; SF-36 = 36-Item Short Form Health Survey; NEO-PI = NEO Personality Inventory; FTND = Fagerström Test for Nicotine Dependence; PEQ = Persisting Effects Questionnaire; SDI = Subjective Drug Intensity; VAS = visual analogue scale; MEQ30 = Mystical Experience Questionnaire (30-item version); 11D-ASC = 11-Dimensional Altered States of Consciousness Rating Scale; EBI = Emotional Breakthrough Inventory; EDI = Ego Dissolution Inventory; AWE = Awe Experience Scale; AE = adverse event.

Blinding

Analyses will be carried out with the treatment groups still blinded and labeled as “group 1” and “group 2”. Before dividing participants, the statistical analysis plan will be completed, signed, and uploaded at [clinicaltrials.gov](#), and the data set locked. The final unblinding of treatment groups (psilocybin or placebo), will not be carried out until all statistical analyses are performed. The last long-term follow up-visit (Week 26) is in April 2026, and this data will be analyzed unblinded.

ANALYSIS

Population

Analyses will follow the intention-to-treat principle i.e., analyzing participants who have been randomized and who have also received a dosing with psilocybin/placebo.

Descriptive statistics

All outcomes will be presented using descriptive statistics, normally distributed data by the mean and standard deviation (SD) and skewed distributions by the median and interquartile range (IQR). Binary and categorical variables will be presented using counts and percentage.

Efficacy analyses

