Analyses will examine associations between selected secondary endpoints and the primary endpoint. These analyses are intended to assess relationships between outcomes and to inform hypotheses regarding potential mechanisms of action. Associations will be evaluated using correlation analyses and/or regression models as appropriate, without adjustment for multiplicity.

- Week 1 neural differentiation between alcohol and neutral cues, quantified using latent variable scores from a mean-centering Partial Least Squares (PLS) analysis of whole-brain blood oxygenation level-dependent (BOLD) responses, and associations with subsequent changes in alcohol consumption and brain-derived neurotrophic factor (BDNF) levels. Resting-state functional connectivity at Week 1 (striatum to salience-network, and within control-network connectivity) and their associations with changes in alcohol consumption and changes in BDNF levels.
- Acute subjective effects during the dosing session and their associations with changes in alcohol consumption and changes in BDNF levels.

Significance level

The primary endpoint will be tested using a one-sided significance level of 0.05 with corresponding 95% confidence intervals, reflecting an a priori directional hypothesis that psilocybin will reduce heavy drinking days compared with placebo. The direction of the primary hypothesis and the use of one-sided testing were prespecified prior to database lock and unblinding and were informed by consistent evidence from prior

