clinical studies. Effects in the opposite direction, if observed, will be fully reported and interpreted descriptively. All secondary and exploratory analyses will be conducted using two-sided significance tests. For Partial Least Squares fMRI analyses, latent variable significance will be assessed via permutation testing (1,000 permutations, $p < 0.05$), with voxel reliability determined by bootstrap ratios $\geq |2.5|$ (200 bootstrap iterations). The PLS analysis will include group (psilocybin vs placebo) as a between-subjects factor, testing for group \times condition (alcohol vs neutral) interactions in whole-brain BOLD responses. Additionally, a separate single-group PLS analysis (collapsing across psilocybin and placebo groups) will be performed to derive individual latent variable scores reflecting each participant's neural differentiation between alcohol and neutral cues. These individual LV scores will be correlated with changes in alcohol consumption from baseline to Week 12. No multiplicity adjustments will be performed, and no additional covariate adjustments will be applied except for the baseline value of the endpoint in question.

Statistical software

All statistical analysis will be performed with R. fMRI data will be preprocessed using fMRIPrep v25.1.0 (<https://fmriprep.org/en/stable/>) and denoised using Nilearn in Python. Partial Least Squares analyses are performed using the Rotman-Baycrest PLS Toolbox in MATLAB. Resting-state functional connectivity analyses will be performed using custom code in MATLAB.

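### The primary endpoint is tested at one-sided 0.05 although the trial was sized on two-sided 0.05, and the 95% interval said to correspond to the test does so only if it is a one-sided bound

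*SAP*

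**What the plan says.** **Sizing (SAP, Sample size).** The sentence opens "Assuming a two" and, after a hyphen and page break, continues "sided alpha level of 0.05 and 90% power, the required sample size was estimated to be 27 participants per treatment arm". The effect is described only as "informed by effect sizes reported in the open-label pilot study"; no number is given. Enrolment follows from it: "Anticipating a dropout rate of approximately 40%, the total planned enrollment was therefore set at 90 participants". After recruitment stopped, a second calculation on the same endpoint and effect size "indicated that 22 participants per treatment arm would provide approximately 85% power, corresponding to a total of 44 completers". No alpha or sidedness is restated for that second figure. The section then reports 59 enrolled and 51 completers.

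**Testing (SAP, Significance level).** "The primary endpoint will be tested using a one-sided significance level of 0.05 with corresponding 95% confidence intervals". The reasons given are a directional hypothesis and consistent earlier clinical evidence. The SAP says this choice was made before database lock and unblinding. An effect in the opposite direction is to be reported in full but interpreted descriptively. For everything else: "All secondary and exploratory analyses will be conducted using two-sided significance tests".

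**Masking (SAP, Blinding).** "Analyses will be carried out with the treatment groups still blinded and labeled as" group 1 and group 2, with treatment identity revealed only when the analyses are finished.

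**Dates.** The last Week 12 visit was on 22 December 2025. The SAP is dated 17 February 2026.

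**The concern.** The rule that decides whether the trial is positive differs from the rule on which it was sized, and the SAP does not acknowledge the difference. Three things follow.

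- **Error rate.** A two-sided 0.05 test allows a 2.5% chance of wrongly claiming benefit. A one-sided 0.05 test allows 5%.
- **Interval.** A one-sided 0.05 test is the counterpart of a two-sided 90% interval or a one-sided 95% bound. If readers are given an ordinary two-sided 95% interval, the test and the interval can disagree on the primary result.
- **Stated power.** The figure of about 85%, used to argue that the trial remained adequate after stopping early, describes a test other than the one that will be run.

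If the result falls between the two thresholds, the trial's conclusion would rest on a choice that its own sample size section does not support.

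**Working it through.** **Inputs.** All are from the SAP except those marked.
- Sizing: two-sided alpha 0.05, 90% power, 27 per arm, 40% dropout, 90 enrolled.
- Revised figure: 22 per arm, about 85% power.
- Completers: 51. *Assumption:* split 25/26, since randomization was 1:1 and completers per arm are not given.
- *Assumption:* a two-group comparison of means with standardized effect d, back-solved because d is not stated.

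**1. Enrolment.** 2 × 27 = 54, and 54 / (1 − 0.40) = 90. This reproduces exactly.

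**2. Implied effect.** By the normal approximation, d = (1.960 + 1.282) × √(2/27) = 0.882. With the noncentral t distribution (df = 2n − 2, noncentrality d√(n/2)), 90% power at 27 per arm needs d = 0.899. If 27 came from rounding up, d could be as high as 0.917, the value at which 26 per arm would already suffice. The range used is 0.899 to 0.917. The 27 per arm cannot itself be checked without the effect size.

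**3. The revised figure at that effect.** By the normal approximation, d√(22/2) = 0.882 × 3.317 = 2.926.
- Two-sided: Φ(2.926 − 1.960) = Φ(0.966) = 83.3%.
- One-sided: Φ(2.926 − 1.645) = Φ(1.281) = 90.0%.

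| Test, 22 per arm | Power at d = 0.899 | Power at d = 0.917 |
|---|---|---|
| two-sided 0.05 | 83.0% | 84.4% |
| one-sided 0.05 | 90.1% | 91.1% |

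Given the two-sided sizing that the SAP states, about 85% fits the two-sided row only. The arithmetic excludes a switch of sidedness between the two calculations; it does not by itself prove that both were two-sided. Had 27 per arm been derived one-sided (d = 0.807 to 0.823), 22 per arm would give 83.9% to 85.1% one-sided. That reading contradicts the SAP's words.

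**4. False claim of benefit.** Two-sided 0.05: 0.05 / 2 = 0.025. One-sided 0.05: 0.05. The ratio is 2.

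**5. Test against interval.** With 51 completers and a model with intercept, group and baseline, df is about 51 − 3 = 48. The critical values are t(0.95) = 1.677 and t(0.975) = 2.011. An estimate of 1.68 to 2.01 standard errors in favour of psilocybin has a one-sided p between 0.025 and 0.05. It is significant under the SAP's rule, yet its two-sided 95% interval includes zero. The repeated-measures model will have somewhat different degrees of freedom, which hardly moves these limits.

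**6. Power with 51 completers.** Noncentrality is d × √(25 × 26 / 51) = d × 3.570, that is 3.209 to 3.273, with df = 49.

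| Test, 25/26 | Power at d = 0.899 | Power at d = 0.917 |
|---|---|---|
| two-sided 0.05 | 88.2% | 89.4% |
| one-sided 0.05 | 93.6% | 94.3% |

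The difference is 5.4 points at the lower d and 4.9 at the upper.

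**The case against.** The SAP has a case. The hypothesis is directional throughout, the choice of a one-sided test is stated openly with reasons, and the document precedes the planned lock and unblinding. Total type I error for the primary endpoint is 5%, because an effect in the wrong direction leads to no claim. A one-sided 95% bound is the exact inversion of a one-sided 0.05 test, so the word corresponding has a coherent reading. The stated power understates the power of the planned test, so nobody is led to think the trial stronger than it is. All of this stands. It can justify a one-sided test, but it does not explain why the level is 0.05 rather than 0.025 when the sizing allowed 2.5% in the favourable direction. Nor does it tell the reader which interval will be reported.

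Stronger readings are tempting but not supported:

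- **A late switch to an easier test.** The SAP postdates the last Week 12 visit, but the protocol is not at hand and may have set one-sided testing earlier. Nothing shows that the choice was made with knowledge of results.
- **An analysis that cannot be run under masked labels.** The estimate, standard error and t statistic can be computed as group 1 minus group 2. The relevant one of two complementary one-sided p-values is then read off at unblinding, with no discretion. At most a sentence is missing.
- **The primary endpoint held to the weakest standard.** Its total error rate equals that of each two-sided secondary test, and the secondary tests are many and unadjusted. Only the favourable-direction threshold is laxer.
- **A revised calculation stated to be two-sided.** The SAP says only that the effect size assumptions were kept. Its sidedness is inferred from the arithmetic.

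**Conclusion.** The point holds as an unreconciled inconsistency in the primary decision rule. Sizing is two-sided 0.05 and testing is one-sided 0.05, and this is plain from the text alone. The consequence is a 5% instead of a 2.5% chance of a false claim of benefit, with total type I error unchanged. That the power figure belongs to the two-sided test rests on taking the SAP's stated sidedness for the 27 per arm and on a simple comparison of means. The conflict with the interval is conditional: it arises if the 95% interval is the usual two-sided one, and the SAP leaves this open. The matter should be settled before lock and unblinding, because it decides what counts as a positive trial and could not credibly be changed afterwards.

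**What to change.** In the Significance level section, before lock and unblinding, specify that the Week 12 difference in percentage of heavy drinking days is tested at two-sided 0.05, or at one-sided 0.025 if the directional hypothesis is to be kept. In either case report the two-sided 95% confidence interval and name it as two-sided. Revise the paragraph justifying one-sided 0.05 to match. State the alpha and sidedness of the 22-per-arm calculation in the Sample size section. Test, interval and stated power then agree.

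The cost is a less favourable threshold, about 2.01 instead of 1.68 standard errors, and about 5 points of power at the planning effect with 51 completers. No data collection changes. As a minor benefit, a two-sided test runs unchanged under the masked labels. If one-sided 0.025 is chosen, add a sentence saying how direction is assigned to the masked groups at unblinding.

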- A mean-centering Partial Least Squares analysis will show a group (psilocybin vs placebo) × condition (alcohol vs neutral) interaction, in the anterior cingulate cortex, insula, striatum, and frontal gyrus where the neural differentiation between alcohol and neutral cues will differ between psilocybin and placebo groups, with reduced differentiation in the psilocybin group. Additionally, in-scan craving ratings following viewing pictures of alcohol (VAS 0-100) will be lower in participants randomized to psilocybin relative to placebo.
- At Week 1, resting-state functional connectivity, defined as Fisher r to z -transformed correlations between BOLD time series extracted from the striatum (defined using the Tian subcortical atlas) and pre-specified regions of the salience network (defined using the Schaefer/Yeo cortical atlas), will differ between participants randomized to psilocybin and placebo.

- **Exploratory hypotheses:**

- Lower Week-1 neural differentiation between alcohol and neutral cues (lower latent variable scores from a separate single-group Partial Least Squares analysis collapsing across treatment groups) will be associated with greater reductions in alcohol consumption from baseline to Week 12. Differences between psilocybin and placebo

groups in striatal functional connectivity (striatum-salience network and striatum-prefrontal) at Week 1 will be associated with changes in alcohol consumption from baseline to Week 12.

- Resting-state functional connectivity in the Control networks (defined using the Schaefer/Yeo cortical atlas) will be lower in the psilocybin group compared to the placebo group at Week 1 and will be associated with changes in alcohol consumption from baseline to Week 12.
- Greater acute subjective effects measured on the dosing day will be associated with greater reductions in alcohol consumption from baseline to Week 12.
- At Week 1, resting-state functional connectivity, defined as Fisher r to z -transformed correlations between BOLD time series extracted from the striatum (defined using the Tian subcortical atlas) and all brain regions (defined using the Schaefer/Yeo cortical atlas), will differ between participants randomized to psilocybin and placebo. Results will be presented as effect sizes i.e., Cohen's D , and inferential statistics i.e., p -values will not be reported.

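### Group-by-condition PLS analysis: 1,000 permutations and 200 bootstraps leave avoidable simulation noise near the cut-offs, which higher counts would largely remove for computing time only

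*SAP*

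**What the plan says.** The SAP lists the cue-reactivity analysis under its secondary hypotheses: "A mean-centering Partial Least Squares analysis will show a group (psilocybin vs placebo") by condition (alcohol vs neutral) interaction, expected "in the anterior cingulate cortex, insula, striatum, and frontal gyrus where the neural differentiation between alcohol and neutral cues will differ" between the groups.

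The decision rules are in the Significance level section. For the latent variable, "latent variable significance will be assessed via permutation testing (1,000 permutations", with p < 0.05 as the criterion. For the voxel map, the bootstrap ratio must reach 2.5 in absolute value, based on "200 bootstrap iterations". The same section says "All secondary and exploratory analyses will be conducted using two-sided significance tests" and makes no multiplicity adjustment.

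On the number of scans, Sample size says "Of these, 28 completed fMRI scans", and only those with complete behavioural data and adequate image quality are kept. The Statistical software section names the PLS toolbox. The SAP gives no random seed, no rule for a borderline result and no reason for the two counts.

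**The concern.** Both resampling results are compared with hard cut-offs. The permutation p-value decides whether a group-by-condition interaction is claimed, and the thresholded map decides which regions are named in support of it. A permutation p-value and a bootstrap standard error are both simulation estimates. With few draws, the same data can give a different answer under a different seed when the result lies close to the cut-off. The SAP does not say which run would then count. Unlike the sampling error from a scan cohort that is already closed, this noise can be made very small by running more draws.

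**Working it through.** **Inputs from the SAP.** Permutations B = 1,000 with p < 0.05; bootstrap iterations B = 200 with ratio at least |2.5| (Significance level); at most 28 scans (Sample size).

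**Step 1: does the stated test keep its level?** Let b be the number of permuted statistics at least as large as the observed one. Both b/1,000 < 0.05 and (b+1)/1,001 < 0.05 reduce to b ≤ 49. The exact size is (49+1)/(1,000+1) = 50/1,001 = 0.04995. The plan's 0.05 is reproduced.

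**Step 2: Monte Carlo error of the p-value.** SE = √(p(1−p)/B). At p = 0.05:
- B = 1,000: √(0.05 × 0.95/1,000) = 0.0069, a 95% range of about 0.036 to 0.064.
- B = 10,000: √(0.05 × 0.95/10,000) = 0.0022.

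**Step 3: chance of each verdict near 0.05.** Here the true p is the value that unlimited permutations of these data would give. P(significant) is the binomial probability of b ≤ 49 for B = 1,000, or b ≤ 499 for B = 10,000.

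| True p | P(significant), B = 1,000 | Wrong side | Two seeds disagree, 2q(1−q) | Wrong side, B = 10,000 |
|---|---|---|---|---|
| 0.040 | 93.4% | 6.6% | 12.4% | about 0 |
| 0.045 | 75.8% | 24.2% | 36.7% | 0.9% |
| 0.055 | 22.5% | 22.5% | 34.9% | 1.2% |
| 0.060 | 7.8% | 7.8% | 14.4% | about 0 |

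The zone in which one run has more than a 2.5% chance of the wrong verdict is 0.037 to 0.064 with 1,000 permutations and 0.046 to 0.054 with 10,000. With 1,000 permutations, two seeds disagree in under 1% of cases at p of 0.03 or below and at 0.07 or above.

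**Step 4: how often does this matter overall?** Step 3 is conditional on a borderline result. Averaging the wrong-side probability over the distribution of p, and assuming an approximately normal two-sided test:

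| Setting | B = 1,000 | B = 10,000 |
|---|---|---|
| No effect | 0.5% | 0.2% |
| 50% power | 1.9% | 0.6% |
| 80% power | 1.3% | 0.4% |

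The power lost by using 1,000 permutations is below 0.2 percentage points.

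**Step 5: Monte Carlo error of the bootstrap ratio.** With approximately normal bootstrap replicates (assumed), the relative error of a bootstrap standard error is 1/√(2(B−1)).
- B = 200: 1/√398 = 5.0%. By the chi-square range, a ratio of 2.5 is estimated between 2.28 and 2.77 (95%). A ratio of 2.4 passes in 22% of runs, and a ratio of 2.6 fails in 20%.
- B = 5,000: 1/√9,998 = 1.0%. The range is 2.45 to 2.55, and both error rates are close to 0.

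**Step 6: comparison with sampling error.** With 28 participants in two groups (26 degrees of freedom), the sampling error of a voxel's standard error is about 1/√(2 × 26) = 14%. Adding the 5% in quadrature gives √(0.139² + 0.050²) = 14.7%, which is about 6% more than the sampling error alone.

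**Step 7: are more permutations available?** Assuming a 14/14 split there are 40,116,600 group relabellings, and at 10/10 there are 184,756. Either leaves ample room for 10,000 draws.

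**The case against.** The strongest reply is that nothing here is wrong. The SAP fixes both counts, both thresholds and the software, and the permutation test has the size it claims. The 24% and 23% apply only when the p-value happens to lie close to 0.05; overall, at most about 2% of verdicts are affected, and those are borderline by any standard. For the map, 14% sampling error outweighs 5% simulation error, so a voxel at 2.4 and one at 2.6 are not meaningfully different with 28 scans. More bootstraps make the map repeatable, not materially more accurate. A seed is usually set in the analysis code.

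All of this stands, and it limits the point in several ways. A reader might infer that the false-positive rate is inflated; step 1 shows that it is not. A reader might infer that about a quarter of verdicts depend on the seed; step 4 shows that this is true only near the cut-off. A reader might extend the point to all the secondary imaging outcomes, but the SAP ties these counts to PLS alone. It does not state that striatum–salience connectivity or in-scan craving ratings use them. Nor does the point reach the exploratory correlation of single-group latent variable scores with drinking change: those scores come from decomposing the observed data and do not depend on either count. Finally, the small scan sample does not make simulation noise more important. It makes it a smaller share of the total error.

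What the reply does not answer is that the noise serves no purpose and can be made very small without touching anything else in the plan.

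**Conclusion.** The point holds as a minor, free improvement to the secondary group-by-condition PLS analysis. The plan contains no error here: the test is valid as written. The verdict can depend on the seed when the true permutation p lies between about 0.037 and 0.064, and this affects about 0.5% to 1.9% of verdicts overall. Near the 2.5 threshold, voxels may enter or leave the map because of the 5% simulation error alone.

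The permutation figures in steps 1 to 3 are exact binomial results, apart from the normal 95% range in step 2. The overall percentages rest on an approximately normal two-sided test, the bootstrap figures on approximately normal replicates, and the 14% on all 28 scans being usable. The missing seed would not be a finding by itself. A fixed seed makes a run reproducible but still dependent on that seed, so it complements higher counts and does not replace them.

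**What to change.** In the SAP's Significance level section, change 1,000 permutations to 10,000 and 200 bootstrap iterations to 5,000 for the group-by-condition PLS analysis. Add one sentence saying that the random seed is set and recorded before the analysis is run. Leave the p < 0.05 criterion and the |2.5| threshold as they are.

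The cost is computing time on at most 28 scans and the edit of two numbers and one sentence. No estimand, threshold, model or sample changes. The imprecision due to the number of scans remains and should still be acknowledged when the map is interpreted.

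### The PLS test of the group × condition fMRI hypothesis fixes neither the centring, nor an interaction contrast, nor the deciding latent variable, and its error rate depends on those choices

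*SAP*

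**What the plan says.** The SAP's Secondary hypotheses predict that "A mean-centering Partial Least Squares analysis will show a group (psilocybin vs placebo) × condition (alcohol vs neutral) interaction" in named regions, and add the direction: "with reduced differentiation in the psilocybin group". The Significance level section states that "The PLS analysis will include group (psilocybin vs placebo) as a between-subjects factor" and says that this PLS is meant to test the interaction across the whole brain. The inferential rule there is that "latent variable significance will be assessed via permutation testing (1,000 permutations" and a threshold of p < 0.05), "with voxel reliability determined by bootstrap ratios" of at least 2.5 in absolute value. The same section says "No multiplicity adjustments will be performed".

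A separate PLS pooled over the arms gives individual cue-differentiation scores, and a GLM repeats the task analysis as an exploratory step. The Statistical software section names the PLS toolbox but no centring option. On numbers, the Sample size section reports: "Of these, 28 completed fMRI scans, however only those with complete behavioural data and adequate quality imaging data for analyses will be retained". The Study design section adds that there was no baseline scan.

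**The concern.** Mean-centred PLS with two groups and two conditions decomposes whatever differences among the four cell means survive the centring. If the cue main effect survives, it competes with the interaction for the LVs. Alcohol and neutral pictures can be expected to produce different responses in both arms, so this is a realistic case.

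Two things can then go wrong. An LV can be significant because of a cue response that the arms share. Less visibly, the LV that does look like the interaction is compared with a reference distribution that does not suit it. What is at stake is the false-positive rate of a prespecified secondary claim that psilocybin alters the neural response to alcohol cues.

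**Working it through.** **Plan's own figure.** The SAP gives a threshold here, not a computed quantity, so there is nothing to reproduce. The starting check is that, with no effect at all, each LV should reject in about 5% of simulated trials. It did, in about 3-7%.

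**What each centring leaves.** Let d₁ and d₂ be the alcohol-minus-neutral mean images in the two arms. The cue main effect is (d₁ + d₂)/2 and the interaction is d₁ − d₂.

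- Each group's own mean removed: cue effect and interaction remain (2 LVs).
- Grand mean removed: group effect, cue effect and interaction remain (3 LVs).
- Condition means removed: group effect and interaction remain (2 LVs).
- Both main effects removed: only the interaction remains (1 LV).

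Only the last makes the LV test a test of the interaction by construction.

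**Simulation.** From the SAP: 28 scans, 2 × 2 design, p < 0.05. Assumed: 14 per arm, 500 voxels with 20% active, the same cue effect in both arms, zero interaction, 400 trials with 1,000 permutations each. Permutation reassigns subjects to groups and swaps conditions within subject, and permuted solutions are not rotated. Each cell gives the percentage of trials with p < 0.05, first without shared noise, then with shared noise of SD 0.2.

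| Centring, LV counted | No cue effect | Cue 0.3 SD | Cue 0.5 SD |
|---|---|---|---|
| Group mean, LV1 | 5.8 / 6.0 | 92.2 / 51.2 | 100 / 100 |
| Group mean, LV2 | 5.0 / 3.7 | 24.0 / 21.5 | 20.0 / 22.0 |
| Group mean, any LV | 10.2 / 9.2 | 92.7 / 62.7 | 100 / 100 |
| Grand mean, any LV | 15.5 / 13.8 | 93.2 / 67.7 | 100 / 100 |
| Condition means, any LV | 11.0 / 8.0 | 8.0 / 11.3 | 6.8 / 7.5 |
| Both main effects, the one LV | 6.0 / 5.0 | 2.2 / 5.2 | 1.8 / 2.5 |

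The simulation error (1.96 standard errors) is about 1.96 × √(0.05 × 0.95 / 400) ≈ 2 points near 5%, and 1.96 × √(0.22 × 0.78 / 400) ≈ 4 points near 22%.

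**Reading the table.**

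1. Under group-mean centring with a cue effect, LV1 is almost the pure cue contrast (median cosine 0.979-0.999 in these runs). With only two dimensions available, LV2 is then essentially the interaction. It rejects in 20-24% of trials although no interaction exists.
2. Under grand-mean centring the cue effect moves to LV2. In a run with 400 voxels and a cue effect of 0.5 SD, LV2 rejected in 100% and LV3 in 19%. Looking at LV1 alone (4%) would hide this.
3. Removing condition means blocks the cue response, but a plain group effect of 0.5 SD then gives a significant LV in 25-34%.
4. With 20 scans in place of 28, LV2 under group-mean centring rejects in 17.7-24.0%, and the interaction-only LV in 0.7-4.3%.

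**Why the interaction-shaped LV is inflated.** In the observed data the cue effect occupies LV1, so LV2 carries the interaction noise, whatever its size. In the permuted data the cue effect is broken up, and LV2 is the smaller of two noise components. As a rough guide, if those two were independent and alike, a cut-off that the smaller one exceeds with probability 0.05 would be exceeded by either one with probability √0.05 ≈ 0.22. That is close to the simulated rates.

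**Range.** A further simulation with 400 voxels put the interaction-shaped LV at about 16-26%, the cue LV at about 11-100%, and the interaction-only test at about 1-7%. With strong shared noise and group-mean centring, the chance that any LV is significant falls to 30-51% for cue effects of 0.3-0.5 SD.

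**The case against.** The SAP does say that the PLS is testing the interaction, and it gives the direction and the regions. It nowhere says that any LV below 0.05 confirms the hypothesis. An analyst who inspects the weights would see that a near-pure cue LV is not the predicted result. The centring is also open: removing both main effects would isolate the interaction, and that choice is compatible with the text. The pooled PLS and the GLM show that the group PLS was not meant as the analysis of the cue response. The finding concerns one secondary hypothesis in at most 28 participants.

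Most of this stands, and it rules out several stronger readings that a reader might infer:

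- That the planned test is shown to be invalid. It is not, because the defect appears under some centrings and not under others, and the SAP does not choose.
- That the false-positive rate for the interaction is 100%. That figure is the rate of detecting a cue effect that was really put into the simulation. It becomes a false claim only if someone misreads the LV.
- That chance ordering of the arms adds an error rate. Which arm has the smaller LV1 weights is roughly a coin flip (44-53% in the simulations), and no stated rule turns on it.

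What does not stand is that careful reading of the weights is enough. The interaction-shaped LV, correctly identified, still rejects at three to five times the nominal rate (16/5 ≈ 3.2 and 26/5 ≈ 5.2) under group-mean or grand-mean centring.

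**Conclusion.** The concern holds as a matter of specification with a measurable consequence. The SAP ties a directional secondary hypothesis to an LV permutation test and leaves open the centring, the contrast and the deciding LV. With a cue response common to both arms and no interaction, the LV that carries the interaction rejects in about 16-26% of trials if only the group mean or the grand mean is removed, against about 1-7% if both main effects are removed. Counting any significant LV, without adjustment, gives about 8-16% under those two centrings even when there is no effect of any kind.

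The sizes rest on assumptions that the SAP does not supply: 14 scans per arm, a cue effect of 0.3-0.5 SD in 20% of 400-500 voxels, the noise structure, and permuted solutions without rotation. The ordering of the options follows from what each centring leaves in the data. The primary endpoint is not affected. This is a cheap improvement.

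**What to change.** In the Significance level section, before the group fMRI analysis is run, prespecify one interaction-only test and base the secondary hypothesis on that single p-value and its direction. Any one of these will do:

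- PLS on cell means with both the group and the condition main effects removed, which leaves one LV;
- non-rotated PLS with the a priori group × condition contrast;
- permutation of group labels on each participant's alcohol-minus-neutral image.

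The three need not give the same p-value, because their permutation schemes can differ. With both main effects removed, permuting groups and conditions gave about 1-5% and permuting group labels alone about 3-6%. So name one test and its permutation scheme. State also how the direction will be read, for example from the alcohol-minus-neutral difference by arm in the named regions, since an LV permutation p-value carries no sign. Report any other LV as descriptive.

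The cost is a few sentences and one re-specified run on the same images. The downside is that the cue main effect has to be reported separately, which the planned pooled PLS and GLM already provide.
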